4.2.2.3 Handling of Dropouts and Missing Data

PK and PD analyses will be based on participants with data available. However, the following imputation methods will be used for descriptive analyses of PK and PD, respectively.

Pharmacokinetics data

Individual concentrations below the LLOQ of the bioanalytical assay will be reported as Not Quantifiable (NQ) in the listings with the LLOQ defined in the footnotes of the relevant tables, figures, and listings (TFLs). Serum concentrations that are NQ or not reported (NR) will be handled as follows for the provision of descriptive statistics:

- Any values reported as NR will be excluded from the summary tables and corresponding figures.
- At a time point where less than or equal to 50% of the concentration values are NQ, all NQ values will be set to the LLOQ, and all descriptive statistics will be calculated accordingly.
- At a time point where more than 50% (but not all) of the values are NQ, the mean, SD, geometric mean, gSD and geometric coefficient of variation (gCV%) will be set to Not Computed (NC). The maximum value will be reported from the individual data, and the minimum and median will be set to NQ.
- If all concentrations are NQ at a time point, no descriptive statistics will be calculated for that time point. The mean, minimum, median, and maximum will be reported as NQ and the gCV% and geometric mean and gSD as NC.
- The number of values below LLOQ ($n < \text{LLOQ}$) will be reported for each time point together with the total number of collected values (n).

- If only two observations are > LLOQ then the minimum and maximum are presented with the other summary statistics as NC.

SARS-CoV-2 Neutralizing Antibodies

The analysis of neutralizing antibody GMT and GMFR will use the following imputation method: a titer value measured below the LLOQ will be imputed to a value that is half of the LLOQ in summaries and analyses but will be listed as reported in the raw data. Titer values measured as above the upper limit of quantification (ULOQ) will be imputed at the ULOQ value.

4.2.2.4 Primary Analysis of Secondary Endpoints

4.2.2.4.1 Pharmacokinetics Data

PK analysis will be based on actual treatment in the PK Analysis Set.

If a participant has any protocol deviation which is identified as a record-level exclusion for the PK analysis in Table 5 of the most recent version of the PDMP, then the PK samples of both compounds collected after the date of deviation and the corresponding derived total concentrations for AZD7442 will be excluded from the analyses.

Due to the change in dosing schedules between CSP V3.0 (dated 09 December 2022) and CSP V4.0 (dated 06 June 2023), there may be visits with a mixture of participants who received and participants who did not receive IMP in previous visit. Therefore, any PK samples from participants who did not receive IMP according to the SoA of CSP V3.0, irrespective of the visit date being before or after the effective date of CSP V4.0 implementation, will be excluded from analyses at all subsequent visits.

PK assessments scheduled for collection pre-dose, but instead collected post-dose at a visit where dosing is done, will be excluded from the analyses. Similarly, PK assessments scheduled for collection post-dose, but collected pre-dose will also be excluded from the analyses.

Individual AZD7442 (AZD8895 and AZD1061) serum concentrations data will be listed and tabulated by mAb component, along with descriptive statistics for the PK analysis set for each treatment group.

Figures of serum concentrations by mAb component and treatment group will also be presented. The figures will include the subset of 20 participants with additional PK measurements.

Potential correlation between PK exposure and safety response may optionally be explored. PK analysis may be performed by the Sponsor and reported in a separate report. The analysis is not covered in this SAP.

4.2.2.4.2 SARS-CoV-2 Neutralizing Antibodies

SARS-CoV-2 nAb analysis will be based on actual treatment in nAb Evaluable Analysis Set. Two (2) assays will be used to provide titers for authentic virus and pseudovirus nAb.

If a participant has any protocol deviation which is identified as a record-level exclusion for the immunogenicity analysis in Table 5 of the most recent version of the PDMP, then their SARS-CoV-2 nAb samples collected after the date of deviation will be excluded from the analyses.

Due to the change in dosing schedules between CSP V3.0 (dated 09 December 2022) and CSP V4.0 (dated 06 June 2023), there may be visits with a mixture of participants who received and participants who did not receive IMP in previous visit. Therefore, any SARS-CoV-2 nAb samples from participants who did not receive IMP according to the SoA of CSP V3.0, irrespective of the visit date being before or after the effective date of CSP V4.0, will be excluded from analyses at all subsequent visits.

SARS-CoV-2 nAb assessments scheduled for collection pre-dose, but instead collected post-dose at a visit where dosing is done, will be excluded from the analyses.

For participants who receive a COVID-19 vaccine after the first dose of IMP, data collected after receipt of the vaccine will also be excluded. Furthermore, for participant who receive a positive SARS-CoV-2 RT-PCR (defined in Section 4.2.3.4.1), data collected after infection will also be excluded, except in the case that SARS-CoV-2 nAb samples were collected during an illness visit.

Descriptive statistics for titer and fold rise will include number of participants, geometric mean, geometric standard deviation (gSD), 95% confidence interval (CI), minimum and maximum. This will be reported separately for nAbs collected during treatment period and illness visits (the illness visits where the series corresponds to positive RT-PCR test, as defined in Section 4.2.3.4.1, will be used in the summary).

A scatter plot of log₂ transformed titers with log₂ transformed serum concentration for each treatment arm, along with the bias-adjusted bootstrapped correlation coefficient, 95% CI and convergence (%) (see Section 4.2.2.2.1).

Summaries will also be split by the previous COVID-19 vaccination status (as defined in Section 4.1.5.1). Samples from 2 separate assays will be analysed using the same methods as described here.

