Week (Month)	-	-	1	4	13 (3M)	14	17 (4M)	26 (6M)	27	30 (7M)	39 (9M)	40	52 (12M)	53	65 (15M)	
Window (days)	-	-	± 3	± 5	± 7	± 3	± 5	± 7	± 3	± 5	± 7	± 3	± 7	± 3	± 15	
P = In-Person Visit RTM = Remote TM Visit ^m	P	P	RTM/ P ^m	P	P	RTM/ P ^m	P	P	RTM/ P ^m	P	P	RTM/ P ^m	P	RTM/ P ^m	P	
Coagulation (predose on days of IMP administration)		X			X			X			X		X		X	8.2.4
FSH (suspected postmenopausal women, < 50 years) ^c	X															5.3, 8.2.4
Nasopharyngeal samples																
Documented negative SARS-CoV-2 RT-PCR test from NP specimen taken ≤ 3 days before Day 1 ^d OR SARS-CoV-2 rapid antigen test (local laboratory)	X ^e															8.2.4
SARS-CoV-2 RT-PCR (central laboratory) (predose)		X ^f														8.2.4

Table 1 Schedule of Activities: Treatment Period – Arm A (AZD7442 Q3M)

Period	Screen ^a	Treatment (Days 1-456)													EoT	For details, see Section
Day (* = IMP dosing day)	-7 to 1	1*	8	29	92*	99	121	183*	190	212	274*	281	365*	372	456	
Week (Month)	-	-	1	4	13 (3M)	14	17 (4M)	26 (6M)	27	30 (7M)	39 (9M)	40	52 (12M)	53	65 (15M)	
Window (days)	-	-	± 3	± 5	± 7	± 3	± 5	± 7	± 3	± 5	± 7	± 3	± 7	± 3	± 15	
P = In-Person Visit RTM = Remote TM Visit ^m	P	P	RTM/ P ^m	P	P	RTM/ P ^m	P	P	RTM/ P ^m	P	P	RTM/ P ^m	P	RTM/ P ^m	P	
Urine samples																
Pregnancy test – urine (WOCBP only) ^g ; (predose on days of IMP administration)	X	X ^h		X	X		X	X		X	X		X		X	5.3, 8.2.4, 8.3.9.1
Urinalysis (predose on days of IMP administration)		X			X			X			X		X		X	8.2.4
PK, PD, ADA assessments																
Serum sample for AZD7442 PK assessment (predose on days of IMP administration unless otherwise noted)		D3 (±1d) ⁱ	D11 (±3d) ^j	X	X		X	X		X	X		X		X	8.5.1
Serum sample for AZD7442 ADA assessment (predose on days of IMP administration)		X		X	X		X	X		X	X		X		X	8.5.2.1

Table 1 Schedule of Activities: Treatment Period – Arm A (AZD7442 Q3M)

Period	Screen ^a	Treatment (Days 1-456)													EoT	For details, see Section
Day (* = IMP dosing day)	-7 to 1	1*	8	29	92*	99	121	183*	190	212	274*	281	365*	372	456	
Week (Month)	-	-	1	4	13 (3M)	14	17 (4M)	26 (6M)	27	30 (7M)	39 (9M)	40	52 (12M)	53	65 (15M)	
Window (days)	-	-	± 3	± 5	± 7	± 3	± 5	± 7	± 3	± 5	± 7	± 3	± 7	± 3	± 15	
P = In-Person Visit RTM = Remote TM Visit ^m	P	P	RTM/ P ^m	P	P	RTM/ P ^m	P	P	RTM/ P ^m	P	P	RTM/ P ^m	P	RTM/ P ^m	P	
Serum sample for SARS-CoV-2 nAbs assessment (predose on days of IMP administration)		X		X	X		X	X		X	X		X		X	8.5.3.1

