8.1.1 Monitoring COVID-19 Symptoms

To capture the incidence of infection, study sites will contact participants monthly (telephone/email/text) as indicated in the SoA (Section 1.3) with reminders to monitor for COVID-19 symptoms. During these monthly contacts the Investigator will enquire about any COVID-19 symptoms (see Table 8) since the previous visit/contact. If such symptoms are evaluated and found to be related to COVID-19 by the investigator, an illness visit will be initiated as soon as possible. Participants who experience suspected COVID-19 symptoms such as those listed in Table 8, will be given instructions to contact the study site.

Participants with suspected COVID-19 symptom(s) after Day 1 will be instructed to initiate Illness Visits and will be tested locally for SARS-CoV-2 (see Section 8.1.3). If negative, the participant will be instructed to stop Illness Visits and continue with the study scheduled assessments for the treatment period (Table 1 for Arm A; Table 2 for Arm B) and follow-up period (Table 3 for both arms). If positive, the participant will be instructed to continue Illness Visits and will have additional assessments per Table 4. Diagnoses of suspected or confirmed COVID-19, confirmed asymptomatic SARS-CoV-2 infection, post-COVID-19 (“long COVID”), or recurrence of COVID-19 (or of SARS-CoV-2 reinfection) will be collected and recorded in the eCRF as an AE (see Section 8.3.5). Post the IL-D90 visit, participants diagnosed with long COVID-19 will have their COVID-19 symptoms reassessed and recorded every 3 months until their symptoms resolve or end of study occurs.

Table 8 COVID-19 Symptoms

Typical presenting symptoms of COVID-19 may include:	
Pediatric 12 - < 18 years of age	Adult ≥ 18 years of age

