8.1.3 Illness Visits

Symptomatic participants (as defined in Section 8.1.1) will be instructed to visit the study site for initiation of illness assessments (Table 4); where supported, home or mobile visits may be substituted for the site visits. Assessments will be performed at IL-D1a for all participants who have reported symptoms of COVID-19 which have been evaluated and found to be related to COVID-19 by the investigator. (Table 4). Assessments will include collection of NP specimens for SARS-CoV-2 rapid antigen and RT-PCR tests (local laboratory; see Sections 8.2.4 and 8.6.1.1) and RT-PCR (central laboratory; see Section 8.6.1.1).

The local laboratory SARS-CoV-2 tests (rapid antigen and RT-PCR) performed at IL-D1a will be used to determine if the participant should continue with the Illness Visits. IL-D1b assessments (ie, blood sample collection) should only be performed if either the SARS-CoV-2 rapid antigen or RT-PCR local test result is positive. If the rapid antigen test result is negative and the RT-PCR is subsequently determined as positive (ie, rapid antigen was false negative), then the participant will be instructed to return to the site, and IL-D1b assessments should be performed as soon as possible (but no later than 2 days) after the positive RT-PCR test result

is available. If the rapid antigen test result is positive and the RT-PCR is subsequently determined as negative (ie, rapid antigen was false positive), the participant will be instructed to discontinue Illness Visits. Only participants with a positive RT-PCR test result will be instructed to continue with the Illness Visits. The results of the SARS-CoV-2 rapid antigen and RT-PCR testing should also be reported to the participant's primary care providers.

Participants will continue with follow-up visits per the SoA for the treatment period ([Table 1](#) for Arm A and [Table 2](#) for Arm B) and follow-up period ([Table 3](#) for both arms). The Illness Visit schedule is to be performed in addition to the scheduled visit in the SoA. Where visits coincide, all assessments from the scheduled visit and Illness Visit should be performed.

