8.5.2.2 SARS-CoV-2 Serology Assessments

Serum samples will be collected to assess SARS-CoV-2 antigen-specific antibody levels. Baseline serostatus and the rate of SARS-CoV-2 infection in participants receiving AZD7442 will be determined by seroconversion (negative to positive) in a validated SARS-CoV-2 N protein antigen assay operated by an authorized laboratory.

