2 CHANGES TO PROTOCOL PLANNED ANALYSES

The CSP details record level exclusions for the nAb evaluable analysis set, following the point at which they receive an alternative COVID-19 monoclonal antibody (mAb). The purpose of an analysis set should be to exclude at the participant level. Therefore, this additional detail has been removed from the analysis set definition in Section 3.2, and record level exclusions for nAb are detailed in Section 4.2.2.4.2. These include exclusions following receipt of an alternative COVID-19 mAb by excluding nAb samples from the date a participant had a protocol deviation recorded for receiving a restricted medication, as detailed in CSP Section 6.5. Although such medications are allowed for treatment of COVID-19 or during the follow-up period (starting ≥ 3 months after the last dose of IMP), nAb samples are also excluded following the date of a positive SARS-CoV-2 RT-PCR (defined in Section 4.2.3.4.1), and nAb samples collected during illness visits are to be summarized separately to main study visits in the planned analyses. Hence this record level exclusion is in line with what was detailed in CSP.

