4.2.3.4 Analysis of Exploratory Endpoints

4.2.3.4.1 SARS-CoV-2 RT-PCR-positive Symptomatic Illness

The incidence of SARS-CoV-2 RT-PCR-positive symptomatic illness will be summarized with descriptive statistics in the FAS at the final data readout only. The number and percentage of participants who have the events will be provided overall and before Day 183, or Day 365.

Participants will be included as an event if they have RT-PCR-confirmed SARS-CoV-2 prior to Day 183, or Day 365, after first IMP dose and present with at least one of the qualifying symptoms as defined in the CSP. A positive SARS-CoV-2 RT-PCR will be defined based on the central laboratory result whenever both central and local laboratory results are available for NP swabs, or if only a central lab NP swab result is available. If only a local NP swab laboratory result is available, then the local laboratory result will be used. If no SARS-CoV-2 RT-PCR results are available, the participant will be considered as not having a RT-PCR-positive symptomatic event. Data from the eCRF will be used to determine if the participant met the qualifying symptoms. If a participant's first case of SARS-CoV-2 RT-PCR positive symptomatic illness occurs on or after Day 183, or Day 365, the participant will be considered as not having an event, respectively. Death due to COVID-19 or hospitalization due to COVID-19 can contribute to this endpoint when a qualifying symptom assessment is not observed.

- For participants with an event after first IMP dose, before Day 183, or Day 365, the date of event will be defined as the earliest symptom onset date from those which triggered an illness visit, where COVID-19 was confirmed with a positive SARS-CoV-2 RT-PCR laboratory test. In the case of death due to COVID-19 or hospitalization due to COVID-19, the date of event is the earliest date of death/date of hospital admission when a qualifying symptom is not observed.

If any of the following censoring reasons are met, the censoring date will be defined as follows:

- Participants who had SARS-CoV-2 RT-PCR positive test prior to first IMP dose will be censored at date of first IMP dose.
- Participants who receive a COVID-19 vaccination after first IMP dose, and prior to having an event before Day 183, or Day 365 will be censored at the date of vaccination.

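### Neutralizing antibody samples are excluded after infection only if RT-PCR was positive, so infections shown only by anti-nucleocapsid seroconversion stay in the GMT, GMFR and nAb-PK correlation

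*SAP*

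**What the plan says.** **Exclusion rule.** SAP 4.2.2.4.2 drops nAb records for protocol deviations listed in the deviation management plan, after a dose not received per CSP V3.0, and when a pre-dose sample was taken post-dose. It also drops them after a COVID-19 vaccine ("data collected after receipt of the vaccine will also be excluded") and after a PCR-proven infection: "for participant who receive a positive SARS-CoV-2 RT-PCR (defined in Section 4.2.3.4.1), data collected after infection will also be excluded". Illness Visit samples are exempt and are summarized separately. SAP Section 2 repeats the RT-PCR trigger. SAP 4.2.3.4.1 defines positivity by nasopharyngeal swab, central result first: "If only a local NP swab laboratory result is available, then the local laboratory result will be used".

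**Who gets an RT-PCR.** In Protocol Tables 1 and 2 the only RT-PCR after screening is the Day 1 predose baseline swab. Later RT-PCRs belong to the Illness Visits in Table 4. Protocol 8.1.1 gives the trigger: "If such symptoms are evaluated and found to be related to COVID-19 by the investigator, an illness visit will be initiated as soon as possible". Protocol 8.1.3 agrees: "Assessments will be performed at IL-D1a for all participants who have reported symptoms of COVID-19", again where the investigator attributes them to COVID-19.

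**Serology.** Protocol 8.5.2.2 says that "the rate of SARS-CoV-2 infection in participants receiving AZD7442 will be determined by seroconversion (negative to positive" in a nucleocapsid assay. That sample is drawn at the same scheduled visits as nAb and at the Early Discontinuation Visit, and SAP Table 3 gives both the same analysis windows. The SAP uses seroconversion only as a separate exploratory incidence endpoint (4.2.3.4.2). SAP 4.2.2.5 plans no sensitivity analysis for PK or PD.

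**The concern.** An infection without reported, investigator-attributed symptoms gets no protocol swab and cannot trigger the exclusion, even when the participant's own serology later shows it. The report could therefore count a participant as infected in one table and, in another, present that participant's later titers as nAb following AZD7442.

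The nAb GMT and GMFR are the secondary pharmacodynamic endpoint. Undetected infections can only accumulate over follow-up, so any upward bias is largest at the later retained visits, where the summaries should show how well repeat dosing maintains titers. The same records enter the correlation in SAP 4.2.2.2.2, which removes Illness Visit samples and values below LLOQ but not seroconverters. In those pairs, part of the titer would not come from the measured drug concentration.

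Missed infections are plausible. The SAP amendment history records that AZD7442 was not active against more than 99% of variants circulating in the USA at the time of the March 2023 request, and that only US participants were enrolled.

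**Working it through.** The plan gives no figure on this point. Its one sample-size figure reproduces (1 - 0.97^100 = 0.952, stated as 95%) but plays no part here.

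**Step 1: which visits are affected.** SAP 4.2.2.4.2 drops nAb samples at all visits after a missed CSP V3.0 dose. Protocol 1.3 describes pathways for a last dose on Day 183 or Day 274. Samples on dosing days are scheduled pre-dose, so the sample at the missed-dose visit itself stays.

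| Pathway | First missed dose | Last retained main-study nAb visit |
|---|---|---|
| Arm A, last dose Day 183 | Day 274 | Day 274 |
| Arm A, last dose Day 274 | Day 365 | Day 365 |
| Arm B, last dose Day 183 | Day 365 | Day 365 |

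On these pathways the bias can build to about 9 or 12 months; Day 456 is already out.

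**Step 2: effect on the geometric mean.** Under SAP 4.2.2.2.2, GMT and GMFR are antilogs of mean log2 values. Let p be the fraction of retained samples at a visit that follow an RT-PCR-missed infection, and g the fold increase in their total measured titer. The mean log2 value rises by p × log2(g), so GMT is multiplied by g^p. GMFR is multiplied by the same factor because the pre-dose titer precedes the infection.

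**Step 3: from own-antibody boost to total titer.** In treated participants the assay reads AZD7442 plus own antibody. If own antibody is a share s of the titer without the infection and infection multiplies it by f, and the two contributions add, then g = 1 + s(f - 1).

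**Step 4: numbers.** The documents give none of p, f or s; all three are assumed.

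| s | f | g | g^0.10 | g^0.20 |
|---|---|---|---|---|
| 10% | 2 | 1.1 | 1.01 | 1.02 |
| 10% | 8 | 1.7 | 1.05 | 1.11 |
| 50% | 2 | 1.5 | 1.04 | 1.08 |
| 50% | 8 | 4.5 | 1.16 | 1.35 |
| 100% | 2 | 2 | 1.07 | 1.15 |
| 100% | 8 | 8 | 1.23 | 1.52 |

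At f = 1 every factor is 1.00. The s = 100% rows are upper bounds for the given p and f, since they assume no drug contribution to the titer. Setting titers above ULOQ to the ULOQ (SAP 4.2.2.3) can only reduce the effect.

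**The case against.** **The SAP does not state the premise.** A reader might infer that the SAP itself accepts that infection raises own antibody. It does not say so. Section 2 introduces the RT-PCR exclusion to show that samples after permitted COVID-19 treatment are still removed, in line with the protocol's alternative-mAb rule. An untreated, undetected infection is outside that purpose. This stands as a point about stated intent. However, the rule in 4.2.2.4.2 applies whether or not the participant was treated, and post-vaccine samples are dropped in the same paragraph. Excluding later samples for active immunity is a reasonable reading of the two rules together.

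**The population may respond weakly.** Participants are enrolled as unable to mount an adequate vaccine response, and AZD7442 contributes to the measured titer. Both argue for a small g. Weak responders may also fail to seroconvert, so serology would miss some infections. Both limits stand, although those whom serology does flag have shown some antibody response.

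**The endpoint is descriptive.** No hypothesis is tested, seroconversion incidence is reported by arm, and monthly symptom enquiry narrows the scope for unreported illness. That lowers the stakes. But an incidence table does not show which titers are affected, and monthly enquiry does not find asymptomatic infection.

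**Exclusion can itself bias.** If infection is likelier at low titers, dropping seroconverters selects better-protected participants and could raise the GMT. This stands, and argues for showing both versions rather than replacing one.

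**Conclusion.** The gap is real. RT-PCR is the only infection trigger, RT-PCR after Day 1 depends on symptoms, and the protocol's own infection marker is measured alongside nAb without being used to exclude nAb records. The deviation plan's exclusion table is not in the documents, but it is described as covering protocol deviations, and seroconversion is not one.

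The size is unknown. With 10% of retained samples affected and a 2- to 8-fold own-antibody boost, the inflation is about 1-5% at s = 10%, 4-16% at s = 50% and at most 7-23% at s = 100%. It is nil if infection adds no titer.

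Two stronger readings are tempting and not supported. One is that contamination builds over the full 15 months to Day 456: on the described termination pathways, the missed-dose rule already removes those samples. The other is that the s = 100% figures, up to 52% at p = 20%, are the expected bias: they treat the whole measured titer as the participant's own antibody. Nor does the point reach the primary safety and ADA endpoints.

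**What to change.** In SAP 4.2.2.4.2, add a second GMT/GMFR table and a second nAb-PK correlation. For participants anti-nucleocapsid negative at baseline, these would also exclude main-study nAb samples from the first anti-nucleocapsid-positive visit onward, or from a positive RT-PCR if earlier. Present them beside the RT-PCR-only results, with the number of samples removed per arm and visit. Amend SAP 4.2.2.5, which now rules out sensitivity analyses, to match.

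The cost is a short text change, one flag from data already scheduled for collection, and a repeat run of the tables and the correlation bootstrap.

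The remedy is partial:
- Late visits will have fewer samples.
- Infections in baseline-positive participants, who may enroll because prior COVID-19 is not an exclusion, cannot be flagged by seroconversion.
- Samples between an infection and the first positive serology stay in, as do those from infected participants who never seroconvert.
- Removing seroconverters may favor better-protected participants, so neither version should stand alone.
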